B. Intervention: The two-step intervention will begin with the patient's primary ED nurse screening for geriatric syndromes. The ED physician will then determine if multidisciplinary intervention is needed and the appropriate level of care (eg, dementia may cause a positive delirium screen, but may not require evaluation if cognitive status is at baseline). Patients requiring multidisciplinary assessment will be either admitted or assigned to the Obs Unit for geriatric assessments based on standard care of their medical problems. These assessments are in addition to usual care for the patient's underlying medical complaint. Geriatric consultation involves evaluation by the hospital's geriatric consultation team: a board certified geriatrician, a geriatric nurse practitioner, and fellows. PT assessments are done by hospital PTs. Medication reviews are completed by ED pharmacists and include confirmation of medication list and dosages and assessment of possible medication interactions or potentially

inappropriate medications using standard criteria.¹ The case management team includes nurse case managers and licensed social workers.

This intervention is already in place, however currently only 5% of older adults in the ED are receiving the screening and only 11% are placed in the Obs Unit for further assessment. Based on data from other institutions, this is likely an underutilized service and we are missing many older adults with acute needs. The goal of implementation is to increase nurse screening to >80% and protocol compliance to >80%.

C. Rationale for study: The data collected for Aim 1 is partly from our baseline ED metrics but also data collected as a result of our accreditation as a Level 1 Geriatric ED. As part of that process, we have to track dispositions, 72 hour return rates, morbidity and mortality reports, readmissions, and geriatric screening rates. This is current monthly report. Additionally, we have to do chart reviews to assess compliance to our geriatric quality protocols. The intervention in question is included as part of our geriatric protocols. This intervention is not "new", it has been ongoing since 2015. However, a formal implementation process is needed as education and accreditation have not been able to increase our screening and compliance rates above 5%. For this reason, [name] took 80 hr of Lean Six Sigma Green Belt training in 2017-2018.

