The research in this study that would not be done normally as part of normal QI at OSU is Aim 2, evaluating the effectiveness of the protocol. Aim 2 will involve recruiting and consenting patients for prospective analysis to determine the impact of the protocol on patient centered outcomes.

Table 2: Study Timeline

Months	Study Phase	Aim 1: Implementation	Aim 2: Effectiveness
0-3	Startup	- Lean team training	Enrollment preparation
3-15	Baseline	- Work flow analyses	- Enroll for baseline cohort (n=150)
16-32	Preparation/Implementation	- Process data collection and Implementation surveys. Lean Six Sigma rapid process improvement	- Follow up and baseline data analysis
33-56	Maintenance/Sustainability	- Continue process data collection - Withdrawal of implementation strategies; Sustainability survey at months 44 and 56.	-Enroll post implementation cohort (n=230) - Data collection and analysis

II. Aim 1 Protocols

A. Specific Aim: Develop, implement, and sustain a two-step intervention providing ED geriatric assessments by combining 1) ED nurse-based screening for geriatric syndromes of all older ED patients with 2) multidisciplinary geriatric assessment in an ED Obs Unit. We will use mixed-methods approaches and the CFIR framework to identify resource, organizational, patient, staff, and administrative factors that affect protocol adherence.²⁻⁴ We will use Lean Six Sigma processes to overcome barriers. We will track effects of the protocol in reference to ED quality metrics, staff work flow, and work culture.

Hypothesis 1a: Implementation: Lean Six Sigma processes will i) increase ED nurse-based screening rates to >80% older adults in the ED and ii) increase protocol fidelity in the Obs Unit to >80%.

Hypothesis 1b: Sustainability: After 6 months of >80% screening, we will characterize the necessary elements for sustainability by systematically withdrawing implementation support strategies. We hypothesize that attention to CFIR elements during implementation will result in routinization and institutionalization that does not significantly decrease with withdrawal or time, as assessed by sustainability surveys.⁵

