B. Subjects: **Aim 1** will include analysis of aggregate ED EMR data on ED patients ≥65 overall (1a) and in the ED obs unit (1b). ED staff and Lean team members are also study subjects for **Aim 1**. All ED and obs unit physicians, midlevel providers, nurses, pharmacists, and involved consultants/stakeholders are eligible, yielding an estimated 260 people. While staff participation in the implementation process and surveys is voluntary, participation in the education and protocol is mandatory.

C. Data Collection: 1) Monthly **aggregate EMR data** on all ED patients is collected as part of general quality measures. This includes: Obs Unit census, patient demographics, geriatric screening results, consultation rates for the multidisciplinary geriatric services, and dispositions from the ED. 2) **Staff Surveys** will be sent electronically using REDCap (Vanderbilt University, TN).^{6,7} There will be at least 2 types of staff surveys: the Implementation survey in Preparation and Implementation phases and the Sustainability scale survey. 3) **Observational data:** Trained observers will perform work flow analyses per usual practice.⁸ The first workflow analysis has already been done and was determined to be IRB exempt as it is a standard QI analysis done for QI purposes.

The only time that identifiable staff information will be used for research purposes will be using staff emails to send out surveys. In keeping with prior practices, all surveys sent to nursing staff will be approved by nursing leadership in addition to the IRB. Individual respondents' emails will be used to allow for paired comparison of survey responses for the sustainability survey at 12 and 24 months after implementation. Otherwise all survey information will be aggregated without identifiers. Survey completion is voluntary and will not affect their work opportunities or be reported to their supervisors. Similarly, staff who are observed during workflow analyses will not have their names reported, but instead will be listed as RN-A1, RN-A2, tech-A1, etc.

D. Aim 1 Timeline/ Methods:

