F.7.iii: *Maintenance and Sustainability (32 months)*: Maintenance: After the goals of >80% screening rate with > 80% protocol fidelity is achieved for 6 months, implementation will be considered successful. The Control/Maintenance phase of the DMAIC process begin. All new nurses and staff will receive the geriatric training. Existing staff will have annual training to review and reinforce their geriatric knowledge. The Lean team will continue to meet monthly, but rapid cycle process improvement will halt unless concerning trends are noted. Sustainability: At 12 and 24 months after Maintenance phase initiation, we will assess the degree of routinization and institutionalization among all 180 ED nurses via a Sustainability survey (estimated response rate 70%).⁵ Implementation support will be withdrawn in a stepwise fashion in 3 month blocks. For example, fidelity audits may be decreased from weekly to monthly to semi-annually. If concerning trends are noted in the monthly aggregate EMR data, these processes will be reinstated and the Lean team will be reconvened. Per STARI guidelines,¹⁰ we will monitor for any contextual changes that occur during this time that may affect results and any adaptations to the protocol. Reporting continued maintenance of a program as the only measure of sustainability is insufficient, as program adaptation may also signal further benefits or sustained improvement.¹¹

III. Aim 2 Protocol

A. Specific Aim: To reduce the decline in functional status and health related quality of life (HRQoL) commonly seen after older adults experience an ED visit.¹²⁻¹⁴ We will recruit cohorts pre and post implementation.

Hypothesis 2a: The intervention will reduce the decline in functional status seen after ED visits. Secondary outcomes include health-related quality of life, ED revisits, and results of the multidisciplinary assessments.

Hypothesis 2b: Patients will be satisfied with the protocol as assessed by thematic analysis of qualitative subject interviews of intervention patients.

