Analysis: Monthly summary statistics on geriatric patient visits, screening and consultation will be recorded. For **Hypotheses 1a.i and 1a.ii (Implementation)** we will calculate the proportions for screening rate and protocol fidelity with 95% CIs monthly using aggregate data. Success is predefined as a point estimate >80% for each outcome for 6 months. The Staff Implementation Surveys (both pre- and post-implementation) will be thematically analyzed using Atlas.ti (Cleverbridge, Inc, Chicago, IL) a qualitative data analysis program, and categorized within the CFIR framework. This data will be used to further the implementation process. Additional assessments of implementation will include: the number of improvement cycles, generated solutions and protocol adaptations, and Lean fidelity. Lean fidelity will be assessed as a yes/no variable at conclusion of implementation. For **Hypothesis 1b, (Sustainability)** we will compare the total mean scores (primary outcome) between the 2 years taking into account linked responses by the same nurses in both years using a mixed model. We will compare individuals' scores over time using a paired t-test or Sign Rank test.

B. Aim 2: Participant representativeness will be assessed by comparison to demographics of all ED patients. The *primary outcome* for Aim 2a is the proportion of patients in the pre and post cohort with a significant (≥ 3 point) decline in Functional Status (OARS) from day 0 to day 90. We will compare proportions with decline in the pre- and post-group using a Chi-square test (primary analysis). Also, logistic regression modeling will be used to compare the functional decline between the pre and post intervention groups univariately and while controlling for initial ED HRQoL, demographic factors (age, race, average socioeconomic status from zip code census tract), Charlson Comorbidity Index score,²³ number of services used and any other significant factors varying between the two cohorts. The total number of covariates will not exceed 12, given we estimate 122 subjects with functional decline. A similar secondary analysis will be done using the 30 day timepoint data.

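### Neither defined Hypothesis 1b measure formally tests whether Step 2 is sustained: the Sustainability survey goes only to the 180 ED nurses and the control-chart rule is set on screening rates only

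*Combined protocol and SAP*

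**What the plan says.** Section II.A sets the aim of developing, implementing and sustaining an intervention whose first step is nurse screening and whose second is "multidisciplinary geriatric assessment in an ED Obs Unit". Hypothesis 1b in the same section predicts "routinization and institutionalization that does not significantly decrease with withdrawal or time, as assessed by sustainability surveys".

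Section I.B describes who does Step 2. On the decision it states: "The ED physician will then determine if multidisciplinary intervention is needed and the appropriate level of care". Delivery falls to the geriatric consultation team, hospital physical therapists, ED pharmacists and a case management team of nurse case managers and social workers.

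On Aim 1 staff subjects, section II.B states: "All ED and obs unit physicians, midlevel providers, nurses, pharmacists, and involved consultants/stakeholders are eligible, yielding an estimated 260 people". Section II.C lists the Sustainability survey among the staff surveys sent by email through REDCap, with email linkage for paired comparison.

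The defined 1b measures are narrower:

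- **Survey population** (II.D, F.7.iii): at 12 and 24 months after Maintenance begins, "we will assess the degree of routinization and institutionalization among all 180 ED nurses via a Sustainability survey", with an expected response of 70%. Table 2 places the surveys at months 44 and 56.
- **Survey analysis** (IV.A, Analysis): total mean scores are compared between the two years, "taking into account linked responses by the same nurses in both years using a mixed model".
- **Control charts** (IV.A, Aim 1b outcome definition): X-bar and R charts are used as support is withdrawn, and a support counts as necessary if its removal significantly lowers screening rates.

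**The concern.** Hypothesis 1b names the surveys as the measure of routinization, and the thing to be sustained has two steps. The survey reaches the profession that performs Step 1. The physicians who decide on Step 2, and the pharmacists and consultants who deliver much of it, are eligible Aim 1 subjects but are not sent it. The control-chart rule also looks at Step 1.

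At stake is what the 1b result can be said to show. Stable nurse scores and stable screening rates could both be observed while consultation after a positive screen becomes less consistent, and neither defined 1b measure would have to register it. The check for mean subscores below 3.0, meant to flag threats to sustainability, draws on the same nurse responses.

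**Working it through.** The plan gives no sample size, power or detectable change for the Sustainability survey, so there is no stated figure to reproduce. The check has two parts.

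**1. Which 1b measure has a criterion on which step**

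| Measure | Where | Step 1 criterion | Step 2 criterion |
|---|---|---|---|
| Sustainability survey, change in total score | F.7.iii; IV.A | Yes, nurses surveyed | No Step 2 professions surveyed, apart from any nurses among the 180 who work in Step 2 |
| Control charts during withdrawal | IV.A, Aim 1b | Yes, screening rate | None |
| Monthly EMR consultation rates | II.C; IV.A | – | Collected, but no 1b rule attached |
| Fidelity audits | F.7.iii | – | Continue, and given as an example of support to be tapered from weekly to semi-annual |

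Section IV.A defines protocol fidelity on Step 2, as the share of screen-positive Obs Unit patients who receive all appropriate consultations. It is a success criterion for Hypothesis 1a (above 80% for 6 months). No matching criterion is carried into 1b. Section II.B ties Obs Unit EMR data to 1b, but IV.A does not turn that into a 1b outcome.

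**2. Head counts and precision**

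Inputs from the plan: 180 nurses and 70% response (F.7.iii); about 260 eligible staff (II.B). My assumptions: all 180 nurses lie within the 260; non-nurses also respond at 70%; two-sided 5% alpha; 80% power; equal SD of change in both groups.

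- Eligible staff not surveyed: 260 − 180 = 80, and 80/260 = 31%.
- Nurse respondents per wave: 0.70 × 180 = 126.
- Respondents per wave if all are surveyed: 0.70 × 260 = 182, of whom 0.70 × 80 = 56 are non-nurses.
- Linked pairs if the same people answer twice: 126 nurses and 56 non-nurses.
- Linked pairs if response is independent between waves (0.70 × 0.70 = 0.49): 0.49 × 180 ≈ 88 nurses and 0.49 × 80 ≈ 39 non-nurses.

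Detectable paired change, in SDs of change, is (1.96 + 0.84)/√n = 2.80/√n:

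| Group | Same people twice | Independent response |
|---|---|---|
| Nurses | 2.80/√126 = 0.25 | 2.80/√88 = 0.30 |
| Non-nurses | 2.80/√56 = 0.37 | 2.80/√39 = 0.45 |

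Detectable difference in change between roles (a role-by-year term) is 2.80 × √(1/n₁ + 1/n₂):

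- Same people twice: 2.80 × √(1/126 + 1/56) = 0.45 SD.
- Independent response: 2.80 × √(1/88 + 1/39) = 0.54 SD.

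For description, the 95% confidence interval for a non-nurse mean at one wave has half-width 1.96/√56 = 0.26 SD of the score. Non-nurse scores can thus be described usefully, but a formal comparison of trends between roles would be weak.

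**The case against.** The best case for the plan is that 1b is operationally about screening. Its text begins from six months of screening above 80%, and IV.A defines the outcome as what is needed to keep screening above 80%. Nurses do the screening, and it starts from 5%. On that reading, surveying nurses fits the stated outcome. This stands as an explanation of the choice. It does not remove the mismatch with II.A, which sets out to sustain both steps and gives the surveys as the measure of routinization without limiting it to Step 1.

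A reader might infer that Step 2 could erode unseen and that the trial would then declare the whole protocol institutionalized. The documents do not support this. Monthly EMR data include consultation rates, process data collection continues through Maintenance, audits continue at lower frequency, and concerning EMR trends lead to reinstated support and a reconvened Lean team. Nor does any section set a rule by which stable survey scores alone establish institutionalization of the whole protocol.

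A reader might also infer that nobody involved in Step 2 is surveyed, or that nurses' answers can say nothing about it. Neither is established. The plan does not say whether Obs Unit nurses or nurse case managers are among the 180, and the survey items are not reproduced.

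Finally, the count of 80 is soft. The 260 is an estimate that includes stakeholders, so not all 80 need work in Step 2, and physical therapy and case management are not named in the eligibility list.

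**Conclusion.** The point holds as a gap in coverage. Hypothesis 1b concerns routinization of a two-step intervention, but neither of its defined measures carries a formal criterion on Step 2. About 80 of an estimated 260 eligible staff (31%), including the physicians, pharmacists and consultants, are outside the survey. That figure rests on all 180 nurses being counted in the 260. What is missing is a formal 1b test of Step 2; monitoring of Step 2 is in place.

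The consequence is confined to how far the 1b conclusion reaches. The Aim 2 primary outcome is not affected. The change is worth making because it is cheap and the staff concerned are already eligible. It would not support a well-powered comparison between roles: with about 39 to 56 linked non-nurse pairs, at an assumed 70% response, only differences of roughly 0.45 to 0.54 SD would be detectable.

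**What to change.** 1. In F.7.iii, send the same REDCap Sustainability survey at months 44 and 56 to all eligible Aim 1 staff, and record role.
2. In IV.A, keep the nurse total score as the primary survey comparison. Report total and subsection scores, including the check for subscores below 3.0, descriptively by role with confidence intervals. Label any role-by-year term exploratory.
3. In the Aim 1b outcome definition, apply the control-chart rule to monthly protocol fidelity as well as to the screening rate. This uses EMR data already in the plan and addresses Step 2 most directly.
4. If the survey is not extended, state that its 1b conclusion is limited to nurse-reported routinization.

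The cost is about 80 more emailed surveys per wave, one more chart, and a few lines of text. The downside is survey burden on physicians and consultants, whose response may fall below 70% and widen the intervals.

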B. Participant Selection: Adults ≥ 65 years assigned to the Obs Unit at the discretion of the treating physician will be enrolled (**n=380**). Patients may be in Obs as part of an Obs protocol (e.g., chest pain) or in response to a positive geriatric screening test. Patients with delirium or dementia will be enrolled with an LAR and patient assent. Exclusion criteria are need for inpatient care, non-English speaking, acute psychiatric issues, prisoners, unable to follow-up, or unable to consent and no LAR.

Study personnel will monitor the Obs Unit electronic tracking board (7am-11pm M-F and select weekends) to identify and recruit 380 patients (150 pre and 230 post cohorts).

C. Data Collection: A survey and chart review will be completed during the Obs stay (Table 3). Follow up phone interviews will occur at days 30 ± 3 and 90 ± 5 . In simulations with research staff, survey completion required 8-10 minutes of patient time. Patient data will be collected in REDCap, which has built in scoring tools for PROMIS measures. Chart abstraction will be done by research coordinators and will use standard methods (including training of abstractors, standardized forms, code book, etc).¹⁵

Data collection definitions:

OARS:¹⁶ (Primary Outcome) An assessment of activities of daily living (functional status) commonly used in ED studies. We will obtain 4 timepoints: Premorbid (patient report of function 1 week prior to ED visit), at the ED visit (day 0), and at days 30 and 90. A change of ≥ 3 points or death between is a significant decline.^{12,17}

HRQoL: The Patient Reported Outcomes Measurement information System (PROMIS) is endorsed by the NIH and PCORI. We will use the Global Health v1.2 (10 questions). A 3 point change is clinically meaningful.¹⁸

New services: Number of new or increased outpatient services (e.g., home health therapies, referral for community interventions, equipment).

New geriatric syndrome¹⁹ diagnoses of delirium, impaired cognition, fall risk, or elder mistreatment.

Geriatric clinic referral: Referrals to the Falls Prevention, Polypharmacy, or Geriatrics Clinic.

Pharmacist recommendations: Number of medication related problems/interactions.^{1,20}

Positive geriatric interventions: ≥ 1 of: new services, diagnoses, referrals, or pharmacist recs.

ED revisits and hospitalizations: Any ED revisits or unscheduled hospitalizations within 90 days.²¹

Patient satisfaction: interview data with themes of positive patient outcomes or satisfaction.

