Table3: Patient level data collected for Aim 2.

	Chart review	Patient interview
Day 0	
 - Demographics and zip code - Charlson Comorbidity Index - Observation protocol - Geriatric screening scores - Geriatric assessments - New geriatric syndromes - Geriatric clinic referrals - Medication recommendations - New services - Disposition and length of stay 	
 - OARS and HRQoL - Current level of care - Falls in the past month - Current home health and community resources - (subset) semi-structured interviews.
Days 30, 90	
 - Clinic referrals and follow-up - ED revisits and 	
 - OARS and HRQoL - Current level of care

	hospitalizations	
 - Falls since last contact - Home health and community resources used
--	------------------	--

Qualitative data: At least 20 patients in the post cohort will be selected for semi-structured interviews. Interviews will be led by a trained researcher coordinator. Purposeful sampling will be used to provide a mix of genders, ages, and Obs Unit dispositions. To assess patient satisfaction, (Aim 2b), a trained researcher will conduct in-person, semi-structured interviews with intervention patients. In addition to Likert-type questions, we will solicit brief descriptions of clinical exemplars of how this intervention produced a positive patient outcome. See interview guide. Maximum variation/heterogeneous purposive sampling will provide a mix of genders, ages, and observation dispositions. This interview will add an additional 20 minutes to the patient's participation time, and so we expect that some participants may decline this portion. With 230 patients in the post implementation cohort, we should have sufficient volume to get at least 20 patients to participate in the qualitative data collection.

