Secondary outcomes for 2a: Dichotomous secondary outcomes will be analyzed using proportions and chi-square tests between pre- and post-intervention groups and with exploratory logistic regression models. Count data will be explored using either Poisson or negative binomial regression. *Exploratory analyses* will use similar methods to compare the pre-intervention group to the post- subgroup who received all 3 screens.

F.12.ii *For Aim 2b,* interviews will be transcribed verbatim and entered into Atlas.ti. We will conduct manifest content analysis of the descriptions using phrases and sentences as our unit of analysis.^{24,25} We will categorize the exemplars and analyze for appropriateness and perceived outcomes based on the level of detail provided. Analysis will include open and axial coding procedures using techniques of constant comparison and questioning within and across cases.^{26,27} The coding schema will be created with consensus on coding definitions and grouping codes into code families/categories. Dual coding with negotiated consensus will be performed on 20% of the data to add rigor to the analysis. Themes will be reported per current guidelines.^{28,29}

V. References

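### The 90-day outcome counts any ED revisit or unscheduled hospitalization, but its only listed source is chart review of unstated coverage, and the follow-up calls list no question on hospital use

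*Combined protocol and SAP*

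**What the plan says.** Hypothesis 2a (section III.A) gives the outcome its role: "Secondary outcomes include health-related quality of life, ED revisits, and results of the multidisciplinary assessments". The definitions in III.C describe it as "Any ED revisits or unscheduled hospitalizations within 90 days", without naming an institution.

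Table 3 assigns each item to a source. For days 30 and 90 the chart-review column reads "Clinic referrals and follow-up - ED revisits and", and the cell continues with hospitalizations. The interview column for those days has four entries: the OARS and HRQoL scales, current level of care, falls ("Falls since last contact"), and use of home health and community services. None asks about ED visits or admissions.

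Patients are contacted at both times: "Follow up phone interviews will occur at days 30" and again at day 90 (III.C), and an LAR or caregiver may join (III.D). On the chart review, III.C says "Chart abstraction will be done by research coordinators and will use standard methods", with training, forms and a code book. It does not say whose records are read. No outside records, information exchange or claims source is mentioned anywhere.

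For analysis, section IV says "Dichotomous secondary outcomes will be analyzed using proportions and chi-square tests between pre- and post-intervention groups", with exploratory logistic regression.

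**The concern.** The definition is wider than the one source listed for it. If the chart holds only this health system's encounters, the outcome actually measured is return to this system, and a patient who goes elsewhere counts as event-free. Apart from HRQoL and the assessment results, ED revisits are the only secondary outcome that Hypothesis 2a names, so the label matters for how the result will be read.

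Two consequences follow if events are lost. A loss of the same proportion in both cohorts weakens the comparison. A loss that differs between cohorts distorts it. The second cannot be excluded, because the comparison is before-and-after: the study timeline puts baseline enrolment in months 3-15 and post-implementation enrolment in months 33-56, so at least 33 − 15 = 18 months separate the end of one from the start of the other. Record coverage or patients' ties to the system could change in that time, and nothing in the plan would detect it.

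**Working it through.** **Reading the definition against the sources.** Table 3 asks the patient about falls and community services, which also happen outside the hospital. It does not ask about hospital use. Current level of care might reveal a patient who is in hospital on the day of the call, but it is a status at one moment and does not record visits since the last contact.

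**Inputs.** The documents give n = 150 (pre) and n = 230 (post). They give no expected revisit rate, no power for this outcome and no capture rate, so there is no plan figure to reproduce. The rates below are assumptions: true 90-day rates p of 20% to 40%, and capture s of 70% to 100%, where s is the share of patients with an event who have one in the chart. The chart is assumed to create no false events.

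**Formulas.** Observed rate q = p × s. Observed risk ratio (post/pre) = (p2·s2)/(p1·s1), so when s1 = s2 it equals p2/p1. Observed difference = p1·s1 − p2·s2, so when s1 = s2 = s it is s × (p1 − p2). The chance of a significant result uses the two-sided 5% pooled-variance normal test.

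**A worked case with no true effect.** Take p = 30% in both, with capture of 80% pre and 70% post.
- q1 = 0.30 × 0.80 = 0.24; q2 = 0.30 × 0.70 = 0.21; difference 0.03.
- Pooled rate = (150 × 0.24 + 230 × 0.21)/380 = 0.2218.
- Null SE = √[0.2218 × 0.7782 × (1/150 + 1/230)] = 0.0436; critical difference = 1.96 × 0.0436 = 0.0855.
- SE at the observed rates = √[0.24 × 0.76/150 + 0.21 × 0.79/230] = 0.0440.
- Chance of rejection = P(Z > (0.0855 − 0.03)/0.0440) + P(Z < (−0.0855 − 0.03)/0.0440) = 0.104 + 0.004 = 10.8%, against a nominal 5%.

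**Results by the same method.**

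| True pre / post | Capture pre / post | Observed pre / post | Risk ratio | Chance of p < 0.05 |
|---|---|---|---|---|
| 30% / 20% | 100% / 100% | 30% / 20% | 0.67 | 60.5% |
| 30% / 20% | 80% / 80% | 24% / 16% | 0.67 | 49.1% |
| 30% / 20% | 70% / 70% | 21% / 14% | 0.67 | 43.3% |
| 30% / 20% | 70% / 80% | 21% / 16% | 0.76 | 24.1% |
| 30% / 20% | 80% / 70% | 24% / 14% | 0.58 | 69.3% |
| 30% / 30% | 70% / 80% | 21% / 24% | 1.14 | 10.2% |
| 30% / 30% | 80% / 70% | 24% / 21% | 0.88 | 10.8% |
| 30% / 30% | 70% / 90% | 21% / 27% | 1.29 | 25.9% |
| 30% / 30% | 90% / 70% | 27% / 21% | 0.78 | 27.5% |
| 40% / 40% | 90% / 70% | 36% / 28% | 0.78 | 37.8% |

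Equal loss leaves the risk ratio at 0.67. The odds ratio, which the exploratory logistic model estimates, moves little: (0.20/0.80)/(0.30/0.70) = 0.58 at full capture and (0.16/0.84)/(0.24/0.76) = 0.60 at 80%. What falls is the difference (10 to 8 to 7 points) and the power. Unequal loss moves every measure, in either direction.

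**The case against.** The strongest case against is that the loss is inferred. The documents do not say which records the chart review covers; the abstraction forms and code book are not reproduced, and the chart might show other hospitals' encounters. That stands. It limits the conclusion to a conditional one, but it does not close the gap, because the plan nowhere says the chart has that coverage.

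Second, Table 3 may be a summary and not the interview script. Death is part of the decline definition in III.C and appears in neither column. So the calls might ask about hospital use without the table saying so. This is possible, but Table 3 is where the protocol assigns items to sources, and it puts this one under chart review.

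Third, a reader might infer that capture will be better in the post cohort because the intervention sends more of those patients to clinics in this system. The documents do not support that. III.C lists clinic referral ("Referrals to the Falls Prevention, Polypharmacy, or Geriatrics Clinic") as a variable to be collected, so whether referral rises is something the study will measure. That referral then raises chart capture is stated nowhere. Post-cohort patients may also be in the Obs Unit on a routine protocol such as chest pain, and the chart method is the same in both cohorts as written. Unequal capture is therefore a possibility of unknown direction.

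Fourth, asking patients has its own weakness. Chart data need no contact, while interview data exist only for those reached. Call completion could differ between cohorts, and recall between calls covers about 60 days in a sample that includes patients with dementia or delirium. This stands and shapes the fix.

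Finally, this is a secondary outcome without stated power, and a 3-point shift is only about 0.03/0.0436 = 0.7 standard errors. That is fair, and it keeps the point modest.

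**Conclusion.** The definition and its only listed source do not match, and the plan does not say whether the chart covers other hospitals. If it does not, outside events are scored as no revisit. Equal loss would cost precision without changing the risk ratio: under the assumed 30% and 20%, the difference falls from 10 to 7-8 points and power from 60.5% to 43-49%. Unequal loss, if it occurs, could create or hide a difference in either direction. With 30% in both cohorts, a 10-point gap in capture produces a 3-point false difference and a false-positive rate of about 10-11%; a 20-point gap produces 6 points and 26-28%.

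These figures rest wholly on assumed event and capture rates. A reader might conclude that outside events are definitely missed, or that the post cohort will be captured better; the documents establish neither. The primary outcome, OARS decline, comes from interviews and is unaffected. The change is worth making because it is cheap and lets the result mean what its label says.

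**What to change.** - Add one item to the day-30 and day-90 interview lists in Table 3: any ED visit or unplanned hospital stay, at any hospital, since the last contact. Ask it identically in both cohorts.
- Define the 90-day outcome as an event found in the chart or reported at interview.
- Report the chart-only result for all patients alongside it, and report call completion by cohort, so that a difference in who was reached is visible.
- State in III.C which institutions' records the chart review covers.
- If the baseline cohort is already complete, do not add the interview source to one side only. Keep chart-only for the comparison and rename the outcome as revisits and unscheduled hospitalizations found in the records reviewed (this health system).

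The cost is one question and one REDCap field on calls already scheduled, with no new contacts. The downside is small: some self-reports will be misdated or not confirmed by a record, and interview capture depends on reaching the patient or caregiver. Reporting the chart-only result beside the combined one addresses that second limit.
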